**Feasibility of exenatide, a GLP-1R agonist, for treating cocaine use disorder: A case series study**

**NCT04941521**

**Version Date: 06/03/2021**

**Protocol Title:** Feasibility of exenatide, a GLP-1R agonist, for treating cocaine use disorder:  
A case series study

**Principal Investigators:** [name], [name]

**Co-Investigator:** [name]

**Study Coordinator:** [name], QA Manager

**Population:** N = 4, male/female, 18-60 years old

**Study Site:** UTHealth Center for Neurobehavioral Research on Addiction (CNRA)

**Study Duration:** 12 months

**Subject Duration:** 7 weeks

---

### General Information

Cocaine use continues to be a significant public health problem with limited treatment options and no approved pharmacotherapies. Glucagon-like peptide 1 (GLP-1) receptors are located in brain areas important for reward and, as such, appear to play a significant role in modulating addictive-like behaviors and drug use (Eren-Yazicioglu et al. 2020). Extended-release exenatide is a GLP-1 receptor agonist approved by the FDA for the treatment of type 2 diabetes. In preclinical studies, exenatide reduces cocaine-seeking and cocaine-taking behavior (Brunchmann et al. 2019). The effect of extended-release exenatide on cocaine use in patients with a cocaine use disorder (CUD) has not yet been investigated. We propose a series of four case studies to collect preliminary data on the feasibility, safety, and clinical effects of exenatide in treatment-seeking patients with CUD.

### Background Information

The U.S. is facing a re-emergence of cocaine as an epidemic drug, indicated by increases in availability, use, and overdose deaths following a previous period of decline (Maxwell 2020). Although significant strides have been made in medication development for the treatment of cocaine use disorder (CUD), no FDA-approved pharmacotherapies are currently available. NIDA's current strategic plan prioritizes efforts to accelerate CUD medication development by rigorously testing novel molecular targets based on a translational research approach. Emerging evidence supports the potential clinical utility of glucagon-like peptide 1 (GLP-1) receptor stimulation for the treatment of substance use disorders, including CUD.

GLP-1 is an incretin hormone that promotes insulin secretion from pancreatic beta cells. Current evidence shows that GLP-1 receptors are widely expressed in areas of the mesolimbic dopaminergic pathway where they regulate the rewarding value of food and drugs of abuse, including cocaine. Preclinical literature suggests that activation of GLP-1 receptors reduces the rewarding effects of cocaine and cocaine self-administration (e.g., Hernandez et al. 2018; Hernandez et al. 2019). In the human laboratory, acute cocaine administration decreases GLP-1 concentrations, with changes associated with subjective reinforcing responses to cocaine ("feeling high, anxious") (Bouhlal et al. 2017). Thus, there is compelling evidence to hypothesize that exenatide treatment will decrease

cocaine use in individuals with CUD. In preparation for conducting a full-scale efficacy trial, the goal of the current proposal is to collect preliminary feasibility, safety, and clinical data on the effects of exenatide in series of four case studies.

### **Study Objectives**

1. To evaluate the feasibility of using exenatide as a treatment for CUD. Primary outcome will be treatment completion, measured as attendance at the end-of-treatment (Week 6) timepoint. Secondary outcomes related to feasibility will include enrollment, attendance, retention, and overall acceptability, measured at study completion (Week 6) timepoint.
2. To evaluate the safety of using exenatide as an adjunct treatment for CUD. Primary outcomes related to safety will include adverse events monitored at each clinic visit.
3. To evaluate clinical effects of exenatide on cocaine use and addiction-related behaviors. Primary outcome related to clinical effects will be cocaine use as measured by urine drug screens at the end-of-treatment (Week 6) timepoint. Secondary outcomes related to clinical effects will include cocaine use as measured by self-report, craving, drug demand, and depressive and affective symptoms assessed during each visit.

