### **Study Design**

The study will employ a case series design with the intervention (extended-release exenatide) run as a single-arm open-label pilot. The framework for this study is exploratory. All participants will receive evidence-based standard of care outpatient treatment for CUD. Primary and secondary outcomes will undergo visual analysis to determine within-subject change as a function of treatment, along with simple descriptive statistics for the group as a whole. At this early planning stage of research on exenatide treatment, a larger scale RCT design was not considered appropriate for feasibility, ethical and methodological reasons.

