### **Study Population**

#### Inclusion criteria:

1. between 18 and 60 years of age
2. meet DSM-5 criteria for current cocaine use disorder as measured by the Structured Clinical Interview for DSM-5 (SCID: First 2015)
3. have at least 1 cocaine-positive urine specimen ( $\geq 150$  ng/mL) during intake
4. be in acceptable health on the basis of interview, medical history and physical exam
5. have hematology and chemistry laboratory tests that are within reference limits ( $\pm 10\%$ ), with the following exception: pancreatic tests (lipase and amylase) must be within normal limits
6. consent to use an acceptable method of birth control during study participation and for one month after discontinuation of the study medication. Non-hormonal methods of contraception are recommended, including barrier contraceptives (e.g., diaphragm, cervical cap, male condom) or intrauterine device (IUD). Steroid contraceptives if used with non-hormonal methods are acceptable
7. be able to understand the consent form and provide written informed consent
8. be able to provide the names of at least 2 persons who can generally locate their whereabouts

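### Objective 3 is worded as an effect of exenatide that this design cannot isolate, and a cocaine-positive urine has two cut-offs (150 ng/mL at entry, 300 ng/mL for the outcome)

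*Combined protocol and SAP*

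**What the plan says.** **Aim and outcome.** In Study Objectives, Objective 3 is "To evaluate clinical effects of exenatide on cocaine use and addiction-related behaviors". Its primary outcome is "cocaine use as measured by urine drug screens at the end-of-treatment (Week 6) timepoint". General Information describes the aim as collecting "preliminary data on the feasibility, safety, and clinical effects of exenatide in treatment-seeking patients with CUD". Objective 1 has its primary outcome at the same visit: "treatment completion, measured as attendance at the end-of-treatment (Week 6) timepoint".

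**Design.** Study Design describes a case series with one open-label arm and an exploratory framework, and says why a randomised trial was not chosen. It plans "visual analysis to determine within-subject change as a function of treatment". Study Procedures gives exenatide on top of six weeks of counselling.

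**Urine cut-offs.** Inclusion criterion 3 requires participants to "have at least 1 cocaine-positive urine specimen" during intake, at 150 ng/mL or above. Description of Outcome Measures codes a urine drug screen as positive at 300 ng/mL of benzoylecgonine or above.

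**Analysis.** Statistics plots individual data, summarises the group descriptively, and rules out testing because the sample is small. It then uses the results to decide whether a larger trial is justified.

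**The concern.** The objective names exenatide as the cause of whatever is observed, but the schedule gives no way to see what counselling alone would have done. Selection adds to this. People who seek treatment and have just given a positive urine may show fewer positives later without any drug effect. The results feed the decision on a larger trial, so a reader of the report could take a fall in use as a signal for exenatide.

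Small numbers, the only reason given for not testing, are a different limit. More participants on this same schedule would narrow the uncertainty but would still not separate exenatide from counselling.

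The two cut-offs raise a second question. The same urine level can count as positive for entry and negative for the outcome. With four participants, one such case moves the group result a long way.

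**Working it through.** The plan gives no power, precision target or expected rate, so there is no stated figure to reproduce. The check compares sections and counts.

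**1. Is there a comparison phase?** In Table 1 the exenatide injection, drug counselling and phone check-in rows sit together. Each shows a blank followed by the same six marks. The urine drug screen row, in the same part of the table, has seven marks. So one urine column comes before the first injection column, and counselling and injections begin together. There is a baseline urine but no counselling-only period. Study Design and Study Procedures add no control group.

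**2. Is the limit stated anywhere?** General Information and Background Information call the data preliminary. Study Design says exploratory. Statistics rules out testing on sample size. No section says that change cannot be separated from counselling or selection. The phrase "visual analysis to determine within-subject change as a function of treatment" does not settle it, because the same section uses the word for standard care ("All participants will receive evidence-based standard of care outpatient treatment for CUD") and for exenatide ("At this early planning stage of research on exenatide treatment").

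**3. Illustration only.** The documents give no rate of positive urines. Assume each participant independently has chance p of a positive Week 6 urine with no drug effect. Then P(at least one negative among four) = 1 − p⁴.

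| Assumed p | 1 − p⁴ |
|---|---|
| 0.9 | 1 − 0.6561 = 34% |
| 0.7 | 1 − 0.2401 = 76% |
| 0.5 | 1 − 0.0625 = 94% |

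Over this range, some negative Week 6 urines are unsurprising without exenatide. The conclusion does not rest on these figures.

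**4. Cut-offs.** Take a participant steady at a level L, with 150 ≤ L < 300 ng/mL.
- Entry: L ≥ 150, so positive.
- Week 6 outcome: L < 300, so negative.
- Group negative rate at Week 6: this person adds 1/4 = 25 percentage points with no change in use.
- Within-subject plot: if the baseline urine is also coded at 300 ng/mL, it is negative too and the plot shows no change. A false improvement appears only if entry status at 150 ng/mL is taken as the baseline.

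**5. Week 6 urine against the series.** Scheduled urines are 7 × 4 = 28, and Week 6 supplies 4/28 = 14%. That denominator includes baseline urines, so the relevant figures are those after the first dose:
- first dose at Week 1: 5 × 4 = 20, and 4/20 = 20%
- first dose earlier: 6 × 4 = 24, and 4/24 = 17%

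The extracted text of Table 1 is split and part of it has lost its week headings, so it cannot settle which applies. That is not a fault in the plan.

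A participant who leaves after Week 4 has no Week 6 value (1 of 4 lost). That person's own count of post-dose urines loses 2 of 5 (40%) or 2 of 6 (33%). The plan gives no rule for a missed urine.

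**The case against.** The strongest reply is that the design is disclosed. The plan calls itself an exploratory, single-arm case series, explains why it is not randomised, places itself before an efficacy trial and rules out testing. The larger-trial decision draws on feasibility and safety as well as cocaine use. The size of any selection effect is unknown, and entry also requires a current diagnosis of cocaine use disorder, not only one positive urine. All of this stands, and it is why the point is minor. What remains is that the objective is worded as an effect of the drug and the attribution limit is never put in words.

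On the cut-offs, eligibility and outcome coding can serve different purposes, and the baseline urine in Table 1 already falls under the 300 ng/mL definition. That stands for the within-subject plots. It does not protect the group's Week 6 negative rate, which has no baseline in it.

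Three stronger readings might be inferred, and the documents do not support them.
- *Only Week 6 is used and the other urines are discarded.* Study Design and Statistics plan within-subject visual analysis and individual plots, so the weekly series can be seen.
- *A count of negative urines should replace Week 6 status.* This is a trade-off. A count pools urines taken early in treatment with those at its end. Pooling over the group makes the count look sturdier when one person leaves after Week 4 (2/20 = 10% or 2/24 = 8% lost, against 25%), but a per-participant count loses 40% or 33% for that person.
- *The plan intends an efficacy conclusion.* No section plans one.

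**Conclusion.** The concern holds in a limited form and is minor. Two things need correcting.

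First, Objective 3 promises an effect of exenatide that cannot be separated from counselling started at the same time or from selection on a positive urine. The plan discloses the design but not this consequence. The evidence is the text and the matching rows of Table 1, and no assumed rate is needed.

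Second, the cut-offs differ. One of four participants steady at 150-299 ng/mL would shift the group's Week 6 negative rate by 25 percentage points with no change in use. This is conditional on such a participant enrolling, and the documents give no frequency. The within-subject plot is unaffected if baseline and later urines share a cut-off.

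The choice of Week 6 status as the named primary is defensible and is not an error.

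**What to change.** 1. Reconcile the 150 ng/mL in the inclusion criteria with the 300 ng/mL in Description of Outcome Measures, and state that the baseline and all later urines are coded at one cut-off.
2. Reword Objective 3 as *change in cocaine use during exenatide plus counselling*. In Statistics, state that change cannot be attributed to exenatide and that the larger-trial decision carries this limit.
3. Optionally, keep the Week 6 urine as the named primary and report beside it each participant's number of cocaine-negative urines out of those scheduled after the first dose, with missed urines shown separately. First confirm the week of the first dose from the intact Table 1, since the denominator is five or six accordingly.

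The cost is a few sentences and, if item 3 is adopted, one descriptive count from urines already scheduled. No visits, samples or tests are added. The downside is a more modest claim.

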### **Study Design**

The study will employ a case series design with the intervention (extended-release exenatide) run as a single-arm open-label pilot. The framework for this study is exploratory. All participants will receive evidence-based standard of care outpatient treatment for CUD. Primary and secondary outcomes will undergo visual analysis to determine within-subject change as a function of treatment, along with simple descriptive statistics for the group as a whole. At this early planning stage of research on exenatide treatment, a larger scale RCT design was not considered appropriate for feasibility, ethical and methodological reasons.

### **Study Population**

#### Inclusion criteria:

1. between 18 and 60 years of age
2. meet DSM-5 criteria for current cocaine use disorder as measured by the Structured Clinical Interview for DSM-5 (SCID: First 2015)
3. have at least 1 cocaine-positive urine specimen ( $\geq 150$  ng/mL) during intake
4. be in acceptable health on the basis of interview, medical history and physical exam
5. have hematology and chemistry laboratory tests that are within reference limits ( $\pm 10\%$ ), with the following exception: pancreatic tests (lipase and amylase) must be within normal limits
6. consent to use an acceptable method of birth control during study participation and for one month after discontinuation of the study medication. Non-hormonal methods of contraception are recommended, including barrier contraceptives (e.g., diaphragm, cervical cap, male condom) or intrauterine device (IUD). Steroid contraceptives if used with non-hormonal methods are acceptable
7. be able to understand the consent form and provide written informed consent
8. be able to provide the names of at least 2 persons who can generally locate their whereabouts

#### Exclusion criteria:

1. current DSM-5 diagnosis for substance use disorder (of at least moderate severity) other than cocaine, marijuana, alcohol, or nicotine
2. current alcohol use that meets for physiological dependence requiring detoxification or makes participation medically unsafe as determined by the medical director
3. have a DSM-5 axis I psychiatric disorder, or anorexia nervosa, or neurological disease or disorder requiring ongoing treatment and/or making study participation unsafe (e.g., psychosis, dementia)
4. significant current suicidal or homicidal ideation
5. Type 1 or type 2 diabetes mellitus (previously diagnosed or indicated by HbA1C level of  $\geq 6.5\%$ )
6. have medical conditions contraindicating exenatide pharmacotherapy (e.g., personal or family history of medullary thyroid carcinoma or multiple endocrine neoplasia syndrome type 2, severe gastrointestinal disease (severe gastroparesis), previous history of pancreatitis or risk of pancreatitis, creatinine clearance  $<45$  or end stage renal disease, previous medically adverse reaction to exenatide or other GLP-1 receptor agonists)
7. taking medications that could adversely interact with exenatide (e.g., oral or injectable blood glucose lowering medications)
8. having conditions of probation or parole requiring reports of drug use to officers of the court
9. impending incarceration
10. pregnant or nursing for female patients

### **Study Procedures**

The study site is the Treatment Research Clinic of the Center for Neurobehavioral Research on Addiction (CNRA), a university-supported center of excellence within the UTHealth Department of Psychiatry and Behavioral Sciences. Established and effective recruitment strategies at the CNRA include newspaper and radio ads, social media posts, referrals from local treatment professionals and former research patients. Those responding to recruitment ads are first screened by phone, then undergo a general intake evaluation protocol (HSC-MS-05-0322) consisting of a drug history and psychiatric evaluation (SCID), physical examination and laboratory testing (chemistry screen, complete blood count, urinalysis, and a 12 lead EKG) prior to signing informed consent to participate in a specific study. For the current study, participants who complete the general intake evaluation protocol and are determined to be eligible will be invited to participate. We expect to screen 10 participants in order to enroll four.

All participants will receive six weeks of treatment as usual (TAU), consisting of standard psychosocial treatment for CUD, delivered by trained masters-level therapists at the CNRA. This treatment will include weekly in-person individual Drug Counseling sessions focusing on providing education and recovery support, according to a standard treatment manual (Crits-Christoph et al. 1999).

The pharmacological intervention (extended-release exenatide) will be given as an add-on to TAU. Exenatide will be purchased commercially as Bydureon® for subcutaneous (SC) injection and administered at a dose of 2 mg once a week for a total of 6 weeks. Per the FDA-approved label, 2 mg of Bydureon is administered SC once a week, at any time of day and with or without meals. Exenatide is supplied as a powder with a solvent for once-weekly injection. Each single-dose, dual-chamber pen contains 0.65 mg of diluent and 2 mg of exenatide, which remains isolated until mixed. Between weekly injection visits, the therapist will conduct a brief (20 minute) phone check-in session with their client to assess functioning, provide support, and encourage ongoing participation. Participants will receive \$15 compensation for attending each weekly study visit plus \$30 for attending the study completion visit at week 6.

### Study medication risks and safety monitoring

Rosenstock and colleagues evaluated extended release exenatide in **non-diabetic** subjects with and without prediabetes. The most common side effect of the treatment was nausea (25%), however, there were no differences in withdrawal rates due to nausea between the treatment and the placebo groups. No serious adverse effects were reported in this study (Rosenstock et al. 2010). A meta-analysis of six randomized controlled trials investigating the use of exenatide in overweight and obese subjects without diabetes reported that there were no serious adverse events in the included studies (Su et al. 2016). There were no episodes of hypoglycemia in the studies that used hypoglycemia as an outcome. The most common adverse events in the exenatide group, included nausea, vomiting, diarrhea, constipation and abdominal distension. Another meta-analysis of the studies investigating GLP-1R agonists in overweight and obese subjects without diabetes reported that GLP-1R agonists did not increase the number of participants who withdrew or dropped out from studies (Zhang et al. 2015). Neither diarrhea nor hypoglycemia appeared more frequently in the GLP-1R agonist group than that in the control group; however, subjects assigned to GLP-1R agonists reported more nausea and vomiting than those in the control group. Collectively, these findings demonstrate that GLP-1R agonist therapy is safe in persons without diabetes, and that the side effect profile of GLP-1R agonists is similar among diabetes and non-DM patients.

Risks associated with study medication will be minimized through careful assessment. During screening, participants will be assessed for contraindications for Bydureon: hypersensitivity to drug/class/components, diabetes mellitus type 1, history of pancreatitis, personal or family history of medullary thyroid cancer or multiple endocrine neoplasia syndrome type 2, creatinine clearance <45 or ESRD. Screening will consist of a detailed medical history and physical exam and blood tests including complete blood count, complete metabolic panel, and pancreatic enzymes levels. Potential participants with diabetes mellitus type 1, creatinine clearance <45 or ESRD, abnormal levels of pancreatic enzymes, those with a history or at risk for pancreatitis, and those with personal and/or family history of thyroid C-cell tumor will be excluded from participation in this study. During the study, participants' vital signs, overall wellbeing, and potential side effects of Bydureon will be assessed at each weekly visit, and finger stick blood glucose levels will be assessed prior to each dose of the medication. Subsequent doses of Bydureon will not be administered if any of the following occur: hypoglycemia (blood glucose <70 mg/dL), severe injection site reaction, hypersensitivity reaction, anaphylaxis, angioedema, cholecystitis, and cholelithiasis or if the Study Physician (Col, [name]) believes that there may be any reason to withhold exenatide.

### Assessment schedule

Table 1 provides a summary of the outcome measures to be completed during the study.

Intake	Enrollment	Treatment (week)						
		0	1	2	3	4	5	6
Informed consent	X							
Eligibility determination (per HSC-MS-05-0322)	X							
Safety labs (amylase/lipase/HbA1C)	X							
Outcome variables								
Treatment participation		X	X	X	X	X	X	
Satisfaction Survey								X
Side effects/AE		X	X	X	X	X	X	
Vital signs/weight	X	X	X	X	X	X	X	
Finger-stick glucose monitoring		X	X	X	X	X	X	

Carbon monoxide (CO)	X	X	X	X	X	X	X
Breath alcohol concentration (BAC)	X	X	X	X	X	X	X
Urine pregnancy test	X	X		X		X	X
Urine drug screen (UDS)	X	X	X	X	X	X	X
Cocaine Timeline Followback (TLFB)	X	X	X	X	X	X	X
Craving	X	X	X	X	X	X	X
Drug Demand	X						X
Beck Depression Inventory II (BDI-II)	X			X			X
Positive/Negative Affect Schedule (PANAS)	X			X			X
Visual analogue scale (VAS) of drug effects	X	X	X	X	X	X	X
Diet	X						X
Intervention							
Exenatide injection		X	X	X	X	X	X
Drug counseling session		X	X	X	X	X	X
Phone check-in session		X	X	X	X	X	X

